5.3. Study participation schedule period of subjects

48 weeks

5.4. Drug information

Aricept® products [Eisai Co., Ltd.]

- 1) Tablets 3 mg, tablets 5 mg, tablets 10 mg (containing 3 mg, 5 mg, 10 mg of donepezil hydrochloride in 1 tablet)
- 2) Fine grain 0.5% (1.0 g contains 5 mg of donepezil hydrochloride)
- 3) D Tablets 3 mg, D Tablets 5 mg, (containing donepezil hydrochloride 3 mg in 1 tablet, 5 mg, 10 mg) D Tablets 10 mg
- 4) Oral jelly 3 mg, oral jelly 5 mg, (containing donepezil hydrochloride 3 mg, 5 mg, 10 mg in 1) oral jelly 10 mg
- 5) Dry syrup 1% (containing 1 mg of donepezil hydrochloride in 1.0 g)

It is possible to change the dosage form during the research period. When changing the dosage form, describe its contents in the case report.

Storage and Storage Conditions

- Storage at room temperature
- Before opening the fine grained bulk package, shield the light and preserve it.
- D tablet After opening the aluminum bag, PTP packing should be stored avoiding moisture. Rose packaging should be stored after opening the aluminum bag, shielding light and avoiding dampness.

For details see Aricept® package insert

5.5. Dose / administration method and administration period / method of use

There line the administration of the following drug agents, to continue 48 weeks.

Once a day as donepezil hydrochloride 3 mg Starting from 1 to 2 weeks 5 mg And orally administered. For advanced Alzheimer's type dementia patients, 5 mg In 4 weeks or more, 10 mg . Further, it should be reduced according to symptoms.

Fine: Normal, for adults once a day 0.6 g Starting from 1 to 2 weeks 1.0 g And orally administered. For advanced Alzheimer type dementia patients, 1.0 g In after more than 4 weeks, 2.0 g . Further, it should be reduced according to symptoms.

Dry syrup: usually, once a day for adults 0.3 g It starts from 0 after one to two weeks. 5 g And orally administered. The high degree of Alzheimer-type dementia, 0.5 g In 4 weeks or more, 1.0 g . Further, it should be reduced according to symptoms.

In addition, if the dose of donepezil hydrochloride is increased or decreased in the range up to 10 mg at the discretion of the doctor in charge of clinical research , the study is continued .

5.6. Assignment method

Assignment managers prepare subject individually allocated envelopes of random assignment of 240 cases of study treatment (including 90 preliminary cases) beforehand and provide them to the clinical research secretariat . Clinical research staff will promptly refer to the clinical research secretariat to allocate examination treatment of the subject in the registration form after consent from the subject is acquired . Clinical research Secretariat, in advance based on the allocation table that was created, and notifies the allocation group that is described in the allocation table by young turn to clinical research personnel. When notifying the assignment, the Clinical Research Secretariat promptly transmits " registration date ", " date of consent acquisition", "subject identification code", "facility name", " name of clinical research staff who made the notification " fill in the allocation record file, stores.

After the subject of allocation query, clinical research personnel, for subjects having acquired the consent, store to create a subject identification code table. In the subject ID code table, fill in the subject name, gender, consent acquisition date, medical record number, subject ID code. The assignment treatment group notified from the clinical research secretariat shall be entered in the subject identification code table promptly after notification .

5.7. Regulations on concomitant medication (therapy)

1) Concomitant medication (therapy)

Not applicable

2) Combination prohibited drug (therapy)

- AChE inhibitors (galantamine , rivastigmine)

3) combination restriction drug (therapy)

Not applicable

4) Combination caution drug (therapy)

Use it with caution when using it.

- Sucamethonium chloride hydrate

It may potentiate muscle relaxant action.

- Choline activator, cholinesterase inhibitor

There is a possibility that the choline stimulating action such as the vagus nerve stimulating action is enhanced.

- Itraconazole, erythromycin, etc., quinidine sulfate hydrate etc.

It may inhibit the metabolism of this drug and potentiate its action.

- Carbamazepine, dexamethasone, phenytoin, phenobarbital, rifampicin etc.

It may promote the metabolism of this drug and reduce its action.

- Central anticholinergic agent, atropine anticholinergic agent

This drug and anticholinergic agent may interfere with each other and reduce the respective effects.

Non-steroidal anti-inflammatory analgesics

It may cause peptic ulcers.

For details see Aricept ® package insert

6. Evaluation item

6.1. Key evaluation items

- 1) Compliance continuation rate when Aricept ® administration after 48 weeks
- 2) The reason at the time of Aricept ® medication discontinuation

6.2. Secondary objectives

- 1) In each group, the analysis of the factors that affect the Aricept ® medication continues

[Subject background factor]

- years of education (number of years)
- Same residence family (Yes No)
- Caregiver background (relationship, sex, age, nursing care experience, watch over / day)
- Nursing care classification (7 categories)
- In-home service (availability, type [free description] , frequency / month)
- Severity : FAST (7 steps)
- MMSE-J total score
- MMSE-J item scores
- Daily independence degree of elderly with dementia (9 ranks)
- Concomitant medications (antipsychotic drugs, antiepileptic drugs, antidepressants, sleep inducing drugs, Chinese herbal medicines etc.)
- Number of concomitant drugs (number)
- BPSD (delusions, hallucinations, excitement, depression · discomfort, anxiety, euphoria, irresponsible · indifference, depression suppression, irritability · instability, presence or absence of abnormal behavior)

[Factors after commencement of research]

- MMSE-J total score change
- MMSE-J The amount of change in each item score
- Average compliance (90 % or more, 70 % or more and less than 90 % , 30 % or more and less than 70 % , 10 % or more and less than 30 % , less than 10 %)
- Addition (presence or absence) of antipsychotic drugs, antiepileptic drugs, antidepressants, sleep inducing drugs, Chinese herbal medicines etc. during the research period
- Addition of memantine during the research period (presence / absence)

2) Safety assessment

- Adverse events
- Side effects

item	Clinical the study start date	Administration start date	2 weeks * 1	12 weeks * 2	24 weeks * 2	48 weeks * 2 Or Canceled * 4	Donepezil hydrochloride when increasing from 5 mg to 10 mg * 5
Acquisition consent	○						
Subject background	○						
Medication compliance			○	○	○	○	○
Medication instruction by 'informed consent file' * 3		○	○	○	○		○
Cognitive function test * 6 (MMSE- J)		△		△	△	△	△
Adverse event			○	○	○	○	○
Use of concomitant medication		○	○	○	○	○	○

7. Observation / inspection items and schedule

7.1. Observation and inspection schedu

Table - 2 Administration and Inspection Schedule

※ 1 Increase from 3 mg to 5 mg of donepezil hydrochloride . The week before the allowable range.

※ 2 Allow 2 weeks before and after .

※ 3 It is implemented in the reinforcement guidance group by "informed consent file" . (Attachment 2)

* 4 Detailed confirmation of the reason for termination is carried out . If you do not visit the hospital, doctor in charge of clinical research, CRC · pharmacist etc investigate until the reason is clarified by telephone etc.

※ 5 It is carried out in advanced Alzheimer's type dementia. From donepezil hydrochloride 5 mg to 10 mg
Is increased.

* 6 When implementation is possible, at the start of administration and at 12 weeks. Furthermore, it is also carried out to the extent possible, at 24 week, 48 week, when stopping, and when increasing from 5 mg to 10 mg of donepezil hydrochloride .

7.2. Observation and inspection items

7.2.1. Subject background

Investigate the following items at the start of clinical research and fill in the case report.

· Subjects Background: gender, date of birth or age, years of education (number of years), family member (presence or absence), caregiver background (relationship, gender, age, presence or absence of nursing experience, watching time / day), requiring long-term care division (7 categories) , in- home service (presence / absence, type [free description] , frequency / month)

· Consent of examinee and substitute : date of consent acquisition , subject identification code

· Disease period: morbidity period, severity FAST Attachment 3) (7th step) , Daily life independence of elderly people with dementia Attachment 4) (9 ranks) ,
Total score of each MMSE-J and each item score, BPSD (delusions, hallucinations, excitement, depression · discomfort, anxiety, euphoria,

excitement / indifference, depression suppression, irritation / instability, abnormal behavior)

- Complications: Name of the afflicted disease at acquiring consent
- Concomitant medication: drug name

7.2.2. View

When administered after 2 weeks, when 12 weeks, at week 24, at 48 weeks or when stopped, and examined the following items during increase from donepezil hydrochloride 5 mg to 10 mg, to fill in the case report form.

1) Medication compliance

The doctor in charge listens to subject compliance and evaluates in the following five stages.

① medication 90 % or more ② medication 70 % or more and less than 90 % ③ medication 30 % or more and less than 70 %

④ medication 10 % or more and less than 30 % ⑤ medication taking less than 10 %

2) Cognitive function test

Examine the total score and each item score of MMSE- J . If practicable, perform at the beginning of administration and at 12 weeks. Furthermore, it is also carried out to the extent possible, at 24 week, 48 week, when stopping, and when increasing from 5 mg to 10 mg of donepezil hydrochloride .

3) Adverse event

9.2 See record of adverse events

Four) Use of concomitant medication

Investigate the drug name. For memantine, we investigate dose and dosing period.

8. End of research , suspension and suspension

8.1. The end of the study

Regarding treatment after completion of this clinical study, we will leave it to the judgment of the attending physician based on the state of the subject .

In the case where the clinical study has been completed in the exemplary medical institutions, research responsible physician based on the provisions of the medical institution, the length and Tokushukai group Co Ethics Committee schematic and terminated that the medical institutions of this clinical study results .

8.2. Stop-interruption in the research

During this clinical study progresses, if it is forced to change, such as stop-interrupted or this clinical study implementation plan of the clinical studies for the following reasons, research investigators length of quickly its contents and the reasons of medical institutions Contact. The responsible physician shall promptly report the relevant information to the head of the medical institution and the Joint Ethics Committee in writing.

- 1) If drug safety agent used, the critical information on the effectiveness obtained
- 2) When it is judged that it is necessary to change this clinical study implementation plan due to the occurrence of serious adverse event
- 3) When it is judged that recruitment of subjects is difficult and it is obviously difficult to achieve the number of cases planned

9. Adverse events and pregnancy information , other events

9.1. Definition

Definitions of adverse events (AE) and serious adverse events (SAE) are shown below.

9.1.1. Adverse event (AE)

The adverse event occurs during this clinical study period to a subject in medicine agent is administered, (including abnormal abnormal laboratory values) any undesirable or unintended sign is that the event, and this clinical study Whether or not there is a cause-and-effect relation does not matter. Including worsening of the original disease, deterioration of complications.

9.1.2. Serious adverse events (Serious adverse event: SAE)

The serious adverse events, of any medical events that occur when drug agent is administered (both doses), refers to the following event.

- 1) Those that resulted in death
- 2) Threatening life
- 3) Those in need of extension of hospitalization or hospitalization / treatment period
- 4) Persistent or serious malfunction
- 5) Congenital abnormality has come

6) Other serious medical events

Medical judgment that medical or surgical treatment is required to expose subjects to crisis or not to result in any of the above, even if death, life-threatening events, or events requiring hospitalization are not occurred Is considered a serious adverse event.

9.2. Record of adverse events

Clinical research physician is, this clinical study for a new adverse events occurring after the start, the event name , serious category (serious, non-serious), severity (mild, moderate, severe) , the expression date, treatment , outcome date (or outcome date confirmed) , outcome (recovery, there has been recovery sequelae, light, non-recovery, death, unknown) and this clinical study causal relationship between (no relation, related Oh might Rukamo , probably related Yes) In the case report.

For abnormal variations in clinical laboratory values judged clinically important by a doctor in charge of clinical research , fill out the case report along with the basis.

Regarding the causal relationship between adverse events and this clinical study , fill in the case report the basis of the judgment.

(1) Causality relationship with this clinical study

1) No relation:

There is no reasonable causal relation between this drug administration and adverse event. (There is no temporal rationality between this drug administration and adverse events, or it is thought that the factors of patients, such as concomitant drugs and original diseases and complications, are greatly influenced by patients.)

2) There may be relevance :

There is a possibility of a reasonable causal relationship between this drug administration and an adverse event. (There is temporal rationality between this drug administration and the adverse event expression and the possibility of a causal relationship with this drug is considered even when considering factors of patients such as concomitant drugs and original diseases and complications Conceivable.)

3) Probably related :

There is a high possibility of a reasonable causal relationship between this drug administration and an adverse event. (There is temporal rationality between this drug administration and the adverse event expression and the possibility of a causal relationship with this drug is

considered even when considering factors of patients such as concomitant drugs and original diseases and complications A similar adverse event is admitted by re - administration.

(2) Severity of Adverse Events

- 1) Mild: degree of discomfort, but not affecting normal daily activities
- 2) Moderate: degree of disruption to normal daily activities due to discomfort
- 3) High level : incapacity or enough to normal daily activities becomes impossible, it was deprived of the activity capacity state

If the severity of an adverse event changes, record the heaviest one.

9.3. Report of serious adverse events

This clinical study regardless of presence or absence of a causal relationship between, if serious adverse events were expressed, investigator physician , after taking prompt and appropriate treatment of safety in the first priority, immediately the medical Report to the chief of the institution.

Brief description of the adverse events, the reason is judged to be severe , the test subject identification code , investigator physician , clinical research name and day 1 of administration , causality (drug agents and clinical studies determined steps) shall describe . In addition, the adverse event will be notified to the joint clinical research institution.

In addition, prepare a serious adverse event report and contact the clinical research secretariat (submission of a copy) . In addition, when unexpected serious adverse events related to this clinical study occur, the status and results of response will be announced and reported to the Minister of Health, Labor and Welfare, etc.

9.4. Reporting of pregnancy information

If you perceive the information about the pregnancy is , the study investigators report on pregnancy and to create, clinical research secretariat to contact the (Submission of copy) . Study principal investigator, and follow-up to the outcome of birth, spontaneous abortion, abortion, etc. pregnancy is known, after the proven outcomes of pregnancy, to create a report on the outcome of pregnancy, clinical research secretariat to contact the (A copy of the Submit) . If the outcome of pregnancy is spontaneous abortion, abortion, congenital anomaly, perinatal mortality, treat it as a serious adverse event, in addition

to a report on the outcome of pregnancy, together with a serious adverse event report create.

9.5. Report of other events

Excessive amount of administration If you perceive the information related to the research principal investigator excessive amount of administration report on the Create, clinical research secretariat to contact the (Submission of copy) .

9.6. Expected adverse events

Please refer to the Aricept ® package insert for the content and rate of occurrence of anticipated adverse events .

9.7. Report to the manufacturer of the drug concerned

The clinical research secretariat submits the following report (copy) to Eisai Co., Ltd., the manufacturer of the drug.

- Serious adverse event report
- Report on pregnancy and report on pregnancy outcome
- Report on overdosage

Ten. Implementation period

Joint Ethics Committee approval after ~ 201 5 years 6 May 3 1 day

Registration period: Joint Ethics Committee approval later - 2014 years 3 Tsuki 31 days

Patient Out Last : 2015 year 3 Tsuki 3 1 day

Statistical analysis: ~ 2015 years 5 May 3 1 day

Summary reporting: ~ 2015 years 6 May 3 0 days

11. Statistical analysis

11.1. Analysis target group

Obtaining informed consent to the procedure noncompliance with examples, all analyzes target excluded from. Aricept ® medication continuation rate , Aricept ® medication discontinuation at the time of the reason for the analysis of, the full analysis (Full Analysis Set : FAS) and the target group which is adapted to study implementation plan (Per Protocol Set : PPS) providing a . FAS is also a one-time study drug is administered has been a subject of the population. PPS shall be a group excluding cases of inappropriate selection / exclusion criteria from FAS and examples of use of

prohibited concomitant medications . In addition, safety on the analysis is , even study drug was administered once a subject of the population.

11.2. Analysis of main evaluation items

48 weeks Aricept between ® medication continuation rate the due to "informed consent file" strengthening leadership group and the normal guidance in group 2 performs a comparison of rates between the groups (two-tailed test, the $p=0.05$, with respect to the following statistical tests Similarly). We also compare intergroups independently in the medication continuation rate for each Visit [2 nd week, 12 th week, 24 th week] .

Aricept ® medication discontinuation during aggregates the reason of, between the groups stop reason to compare .

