Aricept® once, suspended (6 weeks or 4-8 weeks) Then, the case of no treatment cognitive function that is equivalent reported²⁾, compliance continuation rate of Aricept® under the actual clinical, low values (Table - 1). According to the report³⁾ of Watanabe et al., When carried out understanding of drug therapy with pathology and Aricept® of AD, medication instruction classroom with the aim to improve the medication adherence of the (Aricept classroom⁴⁾ to the patient and family, medication continuation rate although the improvement of is Ru recognized, yet, a patient of about 30% in one year has led to discontinuation. In addition, the reason that lead to medication discontinuation of Aricept®, the details are to grasp the unknown is often a (eg. Visits and the like that are no longer), the reason for terminating also in order to address the measures for medication continuation rate improved details There is a need.

Table - 1 medication continuation rate of Aricept ® under real clinical

	Specific usage record survey A ⁵⁾	Specific usage record survey B ⁶⁾			Watanabe 's report ³⁾
Object	Mild	Height			Mainly mild, moderate
Example number	640 cases	824 cases			About 50 cases
period	3 months	6 months	1 year	2 years	1 year
Drug continuation rate	59.7 %	83.7 %	68.9 %	50.9 %	49.2 %
Aricept Classroom Drug continuation rate at the time of implementation					73.1 %

Eisai Co., Ltd., has been created with the patient and family that medication Aricept ® a description for the tool for caregivers "informed consent file". This tool explains the pathology of AD , the significance of medication by Aricept ® , side effects, etc. , and aims to improve the continuation rate of Aricept ® medication by deepening the understanding of patients and their families and carers .

In the present study, strengthening of medication instruction using the tool to verify the impact on the Aricept ® medication continuation rate. In addition, in subjects medication of Aricept ® has reached the stop, investigate the reason for discontinuation in more detail, you analyze the background factor.

As a result of this study, we hope to build a standard dosing guidance method for drug treatment of Alzheimer type dementia and accumulate useful information for measures to improve the medication continuity rate .

2. Purpose of clinical research

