11.5. Other

In addition to the predetermined analysis plan , additional exploratory analysis is performed as necessary, such as comparison between transition patterns of the clinical state after incorporation into the study , as necessary.

12. Number of target cases and setting basis

Total 150 cases

[Rationale for setting]

In one year's observation results ³⁾, which showed the influence on the continuation rate of the medication instruction class (Aricept class) in patients with Alzheimer's type dementia ³⁾, the continuation rate of the group not taking medication instruction was 0.49 (95% confidence limit 0.36 - 0.61), but in the advising instruction classroom the continuation rate was 0.73 (95% confidence limit 0.60 to 0.85). Point estimation of these continuation rate values the group to the detectability 0.8 as when determining the number of necessary cases, 1 group 64 becomes example. Table 3 shows representative values within the confidence limits of the continuity rate of each group and the number of necessary cases for the point estimate. Based on the consideration of the number of these necessary cases and the number of new patients with Alzheimer type dementia in the Tokushu Association Hospital group, the number of target cases was set to 150 cases .

Table - 3 Calculation of the number of necessary examples in the interval estimation range of the medication continuation rate of non-medication / guidance group (detection power = 0.8)

		Medication instruction group						
		0.6	0.65	0.7	0.73	0.75	0.8	0.85
Clothes agents non finger Guiding group	0.35	62	43	31	26	twenty four	18	14
	0.4	97	62	42	35	31	twenty three	17
	0.45	173	96	61	48	41	29	twenty two
	0.49	321	150	85	64	54	37	26
	0.5	388	170	93	70	58	39	27
	0.55	1534	376	163	111	89	54	36
	0.6	-	1471	356	206	152	82	49

13. Ethical matters

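### No severity-adjusted comparison of 48-week continuation is pre-specified although FAST is recorded at study start; adding one is a low-priority precision gain

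*Combined protocol and SAP*

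**What the plan says.** - **Main analysis (11.2).** For 48-week continuation the plan "performs a comparison of rates between the groups", two-sided at 0.05. It lists no covariate or stratification factor and names no test.
- **Allocation (5.6).** The secretariat "notifies the allocation group that is described in the allocation table", working through a pre-made table in order. No stratification by severity is described.
- **Severity.** The entry criteria in 3.1 and 3.2 set no severity limit, and 5.5 and 7.1 provide for advanced patients. FAST is recorded at study start (7.2.1) and is listed in 6.2 as a background factor: "Severity : FAST (7 steps".
- **Use of FAST (11.3).** FAST enters only the logistic regression of factors affecting continuation. That regression is run in each group, and the influence of factors is then compared between groups.
- **Table 1 (section 1).** There are three separate sources: a survey in mild disease (640 cases, 59.7% at 3 months); a survey whose column reads 'Height', apparently advanced disease (824 cases, 83.7% at 6 months, 68.9% at 1 year); and a report of about 50 mainly mild or moderate cases (49.2% at 1 year without the classroom).
- **Sample size (section 12).** Rates of 0.49 and 0.73 with power 0.8 give 64 per group. The target is 150 in total.

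**The concern.** If severity predicts continuation, a comparison that ignores it gives up some precision. With no stratification described, the arms may also differ in severity by chance, and the crude difference then moves with that imbalance. A regression fitted separately in each arm cannot supply the missing estimate, because the instruction effect is not a term in it.

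The practical stake is pre-specification. If the baseline table of a 150-patient trial shows unequal severity, readers will ask for an adjusted result. As the plan stands, that result would fall under the additional exploratory analyses of 11.5 and would be chosen after the data were seen.

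**Working it through.** **1. The plan's own figure.** Inputs from section 12 and 11.2: p1 = 0.49, p2 = 0.73, mean 0.61, two-sided 0.05, power 0.80.

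n = [1.960 × √(2 × 0.61 × 0.39) + 0.8416 × √(0.49 × 0.51 + 0.73 × 0.27)]² / 0.24² = (1.352 + 0.563)² / 0.0576 = 63.6, so 64 per group. This reproduces the plan, and all 48 filled cells of Table 3 also match.

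**2. Power of the crude test at the target size.** With 75 per arm (1:1 is assumed; the ratio is not stated): z = (0.24 × √75 − 1.352) / 0.6686 = 1.087, so power is 86.1%.

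**3. What Table 1 allows for severity.**
- At 1 year, the only common time point: (0.689/0.311) / (0.492/0.508) = 2.29. The gap is 68.9 − 49.2 = 19.7 points.
- At 3 months: continuation cannot rise over time, so the apparently advanced survey was at 83.7% or more. The odds ratio is at least (0.837/0.163) / (0.597/0.403) = 3.5, with a gap of at least 83.7 − 59.7 = 24.0 points. This concerns 3 months, not 48 weeks.
- An odds ratio of 8 is illustrative. No figure in the documents supports it.

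**4. Effect of adjustment on power.** I simulated 40,000 trials per setting with 75 per arm, overall rates 0.49 and 0.73, and one binary severity factor. The advanced share is an assumption, because the documents do not give it. The uncorrected chi-square-type test is compared with the severity-stratified Mantel-Haenszel test.

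| Odds ratio for severity | Advanced share | Crude | Stratified | Change (points) |
|---|---|---|---|---|
| 1 | 20% | 87.0% | 86.3% | −0.7 |
| 1 | 50% | 86.8% | 86.1% | −0.7 |
| 2.29 | 20% | 86.8% | 86.7% | −0.1 |
| 2.29 | 50% | 86.8% | 87.1% | +0.3 |
| 3.5 | 20% | 86.7% | 87.3% | +0.6 |
| 3.5 | 50% | 86.9% | 88.9% | +2.0 |
| 8 | 20% | 86.8% | 89.0% | +2.2 |
| 8 | 50% | 86.8% | 92.5% | +5.7 |

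With equal true rates of 0.49, the crude test rejected in 4.6 to 5.0% of trials and the stratified test in 4.9 to 5.1%. Other runs, with slightly different versions of the crude test, gave 4 to 6%. A logistic likelihood-ratio test at 50% advanced share (6,000 trials per setting) agrees on power: 0.88 vs 0.88 at an odds ratio of 2, 0.87 vs 0.90 at 4, and 0.87 vs 0.93 at 8.

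**5. Chance imbalance.** With advanced share q, the SD of the between-arm difference in that share is √(2q(1 − q)/75). The shift in the treatment difference is that imbalance times the severity gap d.
- q = 0.1, d = 19.7 points: SD 0.049; 95% range ±1.96 × 0.049 × 19.7 = ±1.9 points.
- q = 0.5, d = 19.7 points: SD 0.082; ±3.2 points.
- q = 0.5, d = 24.0 points: ±3.8 points.

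The planned difference is 24 points.

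**The case against.** The strongest reply is that nothing is broken. Randomisation makes the crude test valid, and its error rate already allows for chance imbalance. At 150 patients it has about 86% power against a target of 80%. On the one like-for-like contrast in Table 1 the power gain is essentially nil. The documents also do not show that FAST predicts continuation better than MMSE-J or caregiver factors, which are recorded too. All of this stands, and it is why the point is low priority.

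Two stronger readings are tempting.

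- **That Table 1 shows FAST to be linked to continuation.** It does not. It contains no rate by FAST stage and no comparison by severity within one study. Severity is confounded with source, and the sources differ in population, size and follow-up. Converting the rates to weekly stopping hazards does not help. The mild survey gives −ln(0.597)/13 = 0.040 per week, which would leave exp(−0.040 × 52), about 13%, on drug at 1 year. The mainly mild or moderate column reports 49.2%. That contrast is not a usable severity effect.
- **That adjustment yields a sizeable power gain at no cost.** Gains of several points need odds ratios well above what Table 1 suggests, and a large advanced share. If FAST is not predictive, power falls by a little under 1 point.

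The reply does not touch the gap in pre-specification. A covariate needs only a plausible prior relation to the outcome, and the plan itself lists FAST as a candidate factor.

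**Conclusion.** The point holds as a modest improvement to precision and pre-specification. It does not correct a bias or an invalid test. The documents establish the gap itself: no adjusted between-arm effect is planned, no stratification by severity is described, and FAST is available at study start. Table 1 only suggests, across sources, that severity matters.

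On an odds ratio near 2.3 the change in power is about 0 points. It is 0 to 2 points at 3.5 and 2 to 6 points at 8. The more tangible gain is taking out a shift of about 2 to 4 percentage points either way in the estimated difference. These sizes assume 1:1 allocation, a binary severity grouping, an advanced share of 20 to 50% for power (10 to 50% for imbalance), and the whole cross-source gap credited to severity.

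**What to change.** In 11.2, make the main analysis of 48-week continuation a logistic model with treatment group and baseline FAST as terms. State the FAST grouping once, before analysis, with a rule for a missing FAST value. Report the standardised difference in continuation rates (predicted rates under each group, averaged over all analysed patients) with a 95% CI. Keep the crude two-group comparison as supportive.

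The cost is a few sentences of analysis text; no new data are needed. The downside is a possible loss of up to about 1 point of power if FAST turns out not to predict continuation.
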